3.3 Study Endpoints

3.3.1 Primary Endpoint

Reduction in the number and severity of clinical symptoms associated with EAE after 3 doses of mepolizumab (as compared to symptoms logged in the approximately monthly cycle preceding initiation of mepolizumab).

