During their predicted AEC peak subjects will have Visit 3 to receive clinical evaluation and laboratory testing including whole blood flow cytometry. If the subject has peak eosinophils and neutrophils within a week of each other, Visits 2 and 3 may be combined. At the time of the next predicted AEC nadir (Visit 4), subjects will receive mepolizumab (700 mg IV). History and physical examination, routine laboratory testing, and research samples will be repeated at this visit. At the predicted ANC peak (Visit 5), subjects will have clinical evaluation and laboratory testing research samples. Subjects will also return to the NIH for mepolizumab infusions 1 and 2 months after the first (Visits 6 and 7) and will undergo clinical and laboratory evaluations and receive mepolizumab.

All subjects will be evaluated 1 month after the third mepolizumab infusion at 700 mg for primary and secondary endpoint assessments and to assess clinical benefit. Subjects who receive benefit from mepolizumab (clinical improvement as determined by the investigator) will undergo protocol-specified de-escalation of drug during the Dose De-escalation Phase. Subjects will receive monthly doses of 500 mg (in-person by IV or remotely by SC injection) and then 300 mg SC over the course of 6 months. In-person or remote study visits will continue monthly during de-escalation to assess symptoms and collect blood for clinical and exploratory research evaluations. Subjects may additionally be requested to obtain bloodwork during a symptomatic flare in between monthly visits for safety reasons. Subjects will continue to complete weekly symptom logs, weekly angioedema questionnaires, and monthly quality of life questionnaires during de-escalation.

For all subjects, the end of study visit will be about 1 month after the final study mepolizumab administration and will include safety and research procedures and evaluations.

During the coronavirus disease 2019 (COVID-19) pandemic, subjects may be unable to attend study visits due to travel limitations or safety concerns. In these circumstances, study visits may be rescheduled or modified to allow for remote evaluations (see section [6](#)).

Clinical responders may be eligible to receive compassionate use mepolizumab at the discretion of the investigator and GSK (NCT00244686).

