4.2 Recruitment Plan

EAE is an extremely rare disorder. A maximum of 12 intention-to-treat subjects with EAE will be enrolled with a ceiling of 15 patients for subjects that drop out prior to receiving the first dose. Subjects who are withdrawn prior to receiving mepolizumab will be replaced. The anticipated recruitment period will be 2 years. Subjects will be recruited from those already enrolled on NIH protocol 94-I-0079 (“Eosinophil activation and function in parasitic infections and other conditions with increased tissue or blood eosinophilia in humans”). The NIH is a major referral center for HES, with >200 patients actively followed on protocol 94-I-0079, of which 12 are known to have EAE, and 1-2 new patients referred for evaluation of eosinophilia weekly.

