15.1 Study Hypotheses, Endpoint and Sample Size Justification

This is a pilot study designed as proof of principle, and the small sample size is dictated both by our ability to recruit sufficient numbers of patients in this rare disease and the complexity of the study design.

First, based on the fact that there are n=12 subjects already in the natural history protocol, we expect to be able to get n=5 subjects to participate in this study.

For the primary endpoint of change in maximum daily AE score (DAES), we use a quasi-Poisson model to estimate the average percent reduction after treatment compared to pre-treatment. This model accounts for within-person correlation of

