the repeated maximum DAES by allowing a different (fixed) person effect for each person, and it also allows overdispersion from the Poisson model. Because of the small sample sizes and to be conservative, we allow for overdispersion but not underdispersion and use a t-distribution for inferences. We calculate power to show that the percent reduction is greater than 0. We simulate the maximum DAES values using $n=5$ individuals measured for 4 cycles using a Poisson model with random effects for each individual (to induce within-person correlation) and additional extra-Poisson variation for each observation. Specifically, for the i^{th} individual at the j^{th} cycle, the DAES is distributed Poisson with mean: $a_i * e_{ij} * f_j$, where a_i is distributed gamma with mean 3 and variance 3 (this models the per-person average baseline maximum DAES such that 8% have values less than 1, 58% are less than 3, and 94% are less than 6), e_{ij} is distributed gamma with mean 1 and variance 0.25, and $f_j = 1$ when $j=1$ for the baseline cycle and $f_j = 1-(r/100)$ for the cycles after treatment, where r is the percent reduction. We first simulate 10,000 data sets under the null hypothesis of 0% reduction. The simulated the type I error rate for the two-sided test is 4.9% (close to the nominal 5%); however, the one-sided type I error rate is slightly inflated at 3.4% (for a nominal 2.5%). This slight inflation is due to the small sample size and because of this, we will make two-sided inferences. Next we simulate 10,000 data sets with 87.5% reduction and show that we have over 91% power to show a significant effect at the two-sided 5% level. For the analysis we will present two-sided 95% confidence intervals which can show larger effects than just the difference from 0. For example, the simulations show that with an 87.5% reduction we have 80% power to show that the percent reduction is at least 30% (i.e., 80% of the simulated 95% confidence intervals show percent reductions of at least 30%).

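### The primary endpoint is worded as the effect after three doses, but the primary model and its 91% power describe an average over all post-treatment cycles

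*Combined protocol and SAP*

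**What the plan says.** **Endpoint.** Section 3.3.1, repeated in the Protocol Summary, gives the primary endpoint as "Reduction in the number and severity of clinical symptoms associated with EAE after 3 doses of mepolizumab", with the pre-treatment cycle as comparator. The Précis gives a looser version that counts no doses.

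**Analysis.** Section 15.1 turns this into the maximum daily score (DAES) per cycle: "we use a quasi-Poisson model to estimate the average percent reduction after treatment compared to pre-treatment". The power simulation has n=5 "individuals measured for 4 cycles using a Poisson model with random effects for each individual". The multiplier is 1 in the baseline cycle and 1-(r/100) "for the cycles after treatment, where r is the percent reduction", so each of the three post-treatment cycles gets the same reduction. Section 15.2 adopts this model for the primary analysis. For binary symptoms it uses another window, the first post-treatment cycle only.

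**Timing.** Doses are given at Visits 4, 6 and 7, about 28 days apart, and Visit 8 follows Visit 7 by 28 days (±7). Section 3.2 puts cycle length at about 4 to 6 weeks.

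**Daily logs.** The Protocol Summary, section 6.1 and the footnotes to Table 1 in Appendix B end daily recording at the third dose (Visit 7). Section 7.1.3 continues it to Visit 8.

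**Sample size.** Section 15.1 states "we expect to be able to get n=5 subjects to participate in this study". Section 4.2 states "A maximum of 12 intention-to-treat subjects with EAE will be enrolled".

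**The concern.** Only the interval from Visit 7 to Visit 8 follows three doses. Three post-treatment cycles cannot fit there, so the model must also use cycles that follow one or two doses. Nothing in section 15 restricts it to data after dose 3. The endpoint as worded and the estimate as planned are therefore different quantities unless the effect is constant from the first cycle.

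Two things are at stake. A reader of the results could take the pooled percentage for the effect after three doses. And a literal reading of the endpoint leaves the trial without a power figure, because the stated one was computed for something else. In an open-label study with several candidate windows in the text, the window should be fixed before the data are seen.

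**Working it through.** **Inputs (section 15.1).** Person mean a_i is gamma with mean 3 and variance 3. Extra variation e_ij is gamma with mean 1 and variance 0.25. Counts are Poisson with mean a_i × e_ij × f_j. The analysis is quasi-Poisson with fixed person effects, dispersion not below 1 and a t reference.

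**Formulas.** Let B be the baseline total over subjects, P the post-treatment total and k the number of post-treatment cycles. With fixed person effects and a log link, the fit has a closed form (checked against a standard GLM fit):

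- effect: β = log[(P/k)/B]
- standard error: SE = √[φ(1/B + 1/P)], with φ = max(1, Pearson X²/df)
- residual df = n(k+1) − (n+1)

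The test is the Wald t test, β/SE, unless stated otherwise.

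**Step 1: reproduce the plan (n=5, k=3, df = 20 − 6 = 14; 100,000 simulated data sets).**

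| Quantity | Plan | Recomputed |
|---|---|---|
| Power at 87.5% reduction, two-sided 5% | over 91% | 91% |
| Power to show at least 30% reduction | 80% | 80% |
| Two-sided type I error | 4.9% | 4.8% |
| One-sided type I error | 3.4% | 3.4% |

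The stated figures are correct for the three-cycle average.

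**Step 2: count only the cycle after dose 3 (k=1, n=5, df = 10 − 6 = 4).** Expected totals show the scale of the loss, taking φ = 1 and log(0.125) = −2.08:

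- k=3: B = 5×3 = 15 and P = 15×3×0.125 = 5.6. SE = √(1/15 + 1/5.6) = 0.49, so |β|/SE = 4.2 against a critical t of 2.14.
- k=1: B = 15 and P = 15×0.125 = 1.9. SE = √(1/15 + 1/1.9) = 0.77, so |β|/SE = 2.7 against a critical t of 2.78.

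Simulated power at n=5, k=1:

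- Wald t: 17%
- Wald t, counting an all-zero post-treatment total (19% of data sets) as success: 36%
- Likelihood-ratio F test: 59%
- Showing at least a 30% reduction (Wald): 5%, against 80% with three cycles

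At N=12 (df = 24 − 13 = 11) the single-cycle Wald power is about 95% for an 87.5% reduction, 89% for 75% and 44% for 50%.

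**Step 3: let the effect build up.** The pooled model targets 1 − mean(f_j). The paths below are assumptions; the documents give no per-cycle symptom data.

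| Reduction in cycles 1, 2, 3 | Pooled target | Power n=5 | Power N=12 |
|---|---|---|---|
| 87.5, 87.5, 87.5% | 87.5% | 91% | over 99% |
| 50, 75, 87.5% | 1 − (0.5+0.25+0.125)/3 = 71% | 65% | 96% |
| 0, 87.5, 87.5% | 1 − (1+0.125+0.125)/3 = 58% | 31% | 68% |

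The effect after dose 3 is 87.5% in every row. The pooled target does not depend on sample size.

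**Step 4: what the visit schedule can hold.**

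| Cycle length | Visits 4 to 8 (84 days) | Visits 4 to 7 (56 days) | Visits 7 to 8 (28 days) |
|---|---|---|---|
| 28 days | 3.0 | 2.0 | 1.0 |
| 35 days | 2.4 | 1.6 | 0.8 |
| 42 days | 2.0 | 1.3 | 0.7 |

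The simulated three cycles fit only four-week cycling with logs kept to Visit 8. If logs end at Visit 7, at most two four-week cycles remain and none follows dose 3. Power at n=5 is then 78% (Wald) or 88% (likelihood ratio), again assuming a constant 87.5% reduction.

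**The case against.** The best defence is that the endpoint phrase can mean over the completed three-dose course. The model and the 91% then both fit, and the Précis and section 15.1, which count no doses, lean that way. This reading is possible, but section 3.3.1 does not state it. If it is what was meant, the cure is the same rewording.

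A constant effect is also the plan's own assumption, under which the two quantities coincide. That is correct, and no document shows that symptom benefit builds up.

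Several stronger readings are tempting and are not supported:

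- **Section 3.1 fixes the outcome window.** It has subjects "evaluated 1 month after the third mepolizumab infusion at 700 mg for primary and secondary endpoint assessments". But those assessments include a secondary endpoint defined after the first dose, so the sentence dates the completion of assessments and not the period from which the outcome is drawn.
- **The primary objective asks for the post-dose-3 effect.** Section 2.1 mentions no number of doses; an on-treatment average answers it.
- **The half-life implies build-up.** Drug accumulation is not symptom response. Section 3.1 reports no dose-related difference in maximal blood eosinophil reduction in asthma studies, and section 15.1 plans on an 87.5% eosinophil reduction at the first post-treatment peak.
- **The trial has only 17% power.** That holds for one test, for n=5 and for the literal reading. The Wald test scores a complete absence of symptoms as a failure, and at N=12 the loss largely disappears for an 87.5% effect.

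**Conclusion.** The mismatch is real. The endpoint text names the period after three doses; the primary model estimates one average over all post-treatment cycles, and the stated power is correct for that average only. Taken literally, the endpoint has 17% to 59% power at n=5 and about 95% (Wald) at N=12, for an 87.5% reduction under the plan's own variance assumptions.

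The lasting issue is which effect is estimated. Under a constant effect there is no discrepancy. Under the assumed build-up paths the pooled figure is 71% or 58% when the effect after dose 3 is 87.5%, and more subjects would not change that. Whether build-up occurs is unknown from these documents. That the window includes cycles after doses 1 and 2 is inferred from the four simulated cycles and the visit spacing, since section 15.1 does not say so outright.

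**What to change.** 1. In the Protocol Summary and section 3.3.1, restate the primary endpoint as the average reduction in maximum DAES over all cycles from the first dose through Visit 8, against the pre-treatment cycle. This is what the model and the power describe.
2. Make the Protocol Summary, section 6.1 and the Appendix B Table 1 footnote agree with section 7.1.3, so that daily logs run through Visit 8. Without this, neither the restated window nor any post-dose-3 estimate from the daily log can be produced.
3. State in section 15 that the number of post-treatment cycles depends on cycle length: about 3 in 84 days for four-week cycles, but 2.0 to 2.4 for five- to six-week cycles.
4. Name the post-dose-3 cycle against baseline as a supportive estimate, from the same model with a separate effect for each post-treatment cycle. Do not describe the pooled estimate as the effect after three doses.

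**Cost.** About one more month of daily logging where it would have stopped at Visit 7, some rewording and one extra model fit. The supportive estimate will be imprecise at n=5, and for cycles longer than 28 days it rests on a partial cycle.

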1.1 Background Information

EAE, also known as Gleich's Syndrome, is characterized by recurrent episodes of urticaria, fever, angioedema, weight gain, and dramatic eosinophilia that occur at 3- to 6-week intervals and resolve with spontaneous diuresis in the absence of therapy (1). The dramatic waxing and waning of clinical manifestations, which can include shifts in weight of up to 40 pounds, has a significant impact on the lives of patients with EAE. Although conventional HES therapies, including glucocorticoids, are effective in reducing symptoms, the toxicity of these therapies limits their long-term use in EAE.

EAE is an extremely rare disorder. Among 303 consecutively enrolled subjects on our natural history protocol studying eosinophilic syndromes (94-I-0079), 12 subjects with EAE were identified. The estimated prevalence of HES is 0.036/100,000 persons based on coding in the SEER (Surveillance, Epidemiology, and End Results Program) database, although this is likely underestimated due to the lack of specific International Classification of Diseases codes for HES (2). Assuming that the proportion of referrals to NIH for EAE reflects the proportion of such patients in the general HES population, the prevalence of EAE is estimated to be 0.012-0.2/100,000 persons in the United States. This low prevalence has precluded clinical treatment studies in EAE to date.

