3.2 Study Schematic

A general schematic for the primary and secondary assessments on the study is given below. Cycle duration varies between subjects, but is approximately 4-6 weeks (examples of cycle length determination based on data from individual subjects are given in [Appendix D: Cycle Length Determination for 3 Patients](#)). Study dose de-escalation is not shown.

[figure not shown]

Figure 1. Study Schematic.

The black arrows indicate study visits (V) for blood draws and clinical assessments, the purple arrows indicate mepolizumab infusions, and the blue bars indicate interval blood draws being performed locally. The estimated timing of visits is indicated in approximate days (~D). The asterisks (*) and (**) define the comparison timepoints for the secondary efficacy endpoint. Subjects will document their weight, temperature, and symptoms and severity every day for about 3 months after enrollment. V8 will begin the Dose De-escalation Phase for subjects who receive benefit from mepolizumab.

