6.3.4 Mepolizumab administration (Visit 6)

Visit 6 will be scheduled 28 days (\pm 5 days) after Visit 4.

The following procedures and laboratory tests will be performed:

- Targeted history and physical examination, including limb measurements
- Vital signs, including weight
- Review of symptom/weight logs and patient-reported outcome measures adherence
- CBC with differential
- Routine laboratory testing, including acute care panel, hepatic panel, mineral panel, LDH, CPK, CRP, and urinalysis
- Urine pregnancy test (females of childbearing potential only)
- Serum tryptase, aldolase, and quantitative immunoglobulin levels (including IgE)
- Serum or plasma and urine for eosinophil granule protein and mediator levels
- Collection of whole blood for purification and storage for research studies
- AE assessment

Following completion of the evaluations and pregnancy testing (if applicable), mepolizumab 700 mg IV will be administered in the Day Hospital.

There will not be additional at-home blood or urine collections under this protocol after Visit 6.

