6.3.5 Mepolizumab administration (Visit 7)

Visit 7 will be scheduled for 28 days (± 5 days) after Visit 6. The following procedures and laboratory tests will be performed:

- Targeted history and physical examination, including limb measurements
- Vital signs, including weight
- Review of monthly patient-reported outcome measures adherence
- CBC with differential
- Routine laboratory testing, including acute care panel, hepatic panel, mineral panel, LDH, CPK, CRP, and urinalysis
- Urine pregnancy test (females of childbearing potential only)
- Serum tryptase, aldolase, and quantitative immunoglobulin levels (including IgE)
- AE assessment

Following completion of the evaluation and pregnancy testing (if applicable), mepolizumab 700 mg IV will be administered in the Day Hospital.

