6.3.6 Completion of primary and secondary endpoint assessments (Visit 8)

Visit 8 will again be scheduled 28 days (± 7 days) after Visit 7. This visit may occur over several days.

The following procedures and laboratory tests will be performed:

- Targeted history and physical examination, including limb measurements
- Vital signs, including weight
- CBC with differential
- Routine laboratory testing, including acute care, hepatic, and mineral panels, CRP, and urinalysis
- Serum tryptase, aldolase, and quantitative immunoglobulin levels (including IgE)
- Collection of serum or plasma and urine for immunologic analyses and quantification of eosinophil granule proteins
- Collection of whole blood for isolation and storage of plasma and cells for research studies
- Whole blood lymphocyte phenotyping (TBNK) and RNAseq
- Optional bone marrow biopsy and aspiration, requested of subjects for whom a sample was collected/available prior to study treatment (may be done once at any time while on study drug)
- AE assessment

After completion of the procedures described above, subjects who have received benefit from mepolizumab administration will begin the Dose De-escalation Phase (Visits 8-14, as outlined in section [6.4](#)).

For subjects who do not participate in the Dose De-escalation Phase, Visit 8 will be the end of study visit.

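### Post-treatment cycles in the primary analysis are undefined, and three of them do not fit the 84-day follow-up of subjects with 5- or 6-week cycles

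*Combined protocol and SAP*

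**What the plan says.** Section 3.3.1 compares symptoms after three doses with a single pre-treatment cycle ("as compared to symptoms logged in the approximately monthly cycle preceding initiation of mepolizumab"). Section 15.1 takes the maximum DAES per cycle and simulates "individuals measured for 4 cycles using a Poisson model with random effects for each individual": one baseline cycle and three after treatment. Section 15.2 adds a sensitivity analysis on the sum of the DAES per cycle.

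On cycle length, section 1.1 says that episodes "occur at 3- to 6-week intervals and resolve with spontaneous diuresis". Section 3.2 says "Cycle duration varies between subjects, but is approximately 4-6 weeks".

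The post-treatment calendar follows the dosing interval. Section 6.3.4 has "Visit 6 will be scheduled 28 days" after Visit 4, section 6.3.5 has "Visit 7 will be scheduled for 28 days" after Visit 6, and section 6.3.6 has "Visit 8 will again be scheduled 28 days" after Visit 7. The windows are 5, 5 and 7 days either way. Section 6.3.3 accepts that the drug may change cycle times while infusions stay about a month apart.

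The end of daily logging is stated in two ways. The Protocol Summary, section 6.1 and the footnote to Table 1 in Appendix B end it at the third dose (Visit 7). Section 7.1.3 runs it to Visit 8.

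**The concern.** The cycle is the unit of analysis for the primary endpoint, and it is defined only before treatment. Visits 2 to 4 are timed to the subject's own neutrophil peak, eosinophil peak and eosinophil nadir, so the baseline cycle contains a flare by design. Nothing gives the same guarantee afterwards.

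For a subject with a 5- or 6-week cycle, either reading breaks something that the plan states. Natural cycles cannot supply the three post-treatment values in the power model. Windows of about a month are shorter than the cycle, so some can miss the flare, and a maximum taken over such a window is low whether or not the drug works. The trial has no control arm to absorb this, and the simulation in section 15.1 does not include it.

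**Working it through.** **Inputs from the documents.** Cycle lengths, visit spacing and windows are as given above. The first dose is at the eosinophil nadir, about 16 days after the neutrophil peak (7 + 9 days, section 1.1; Day 15 in Table 1). The score model in section 15.1 has a person mean that is gamma with mean 3 and variance 3, an extra gamma factor with mean 1 and variance 0.25, and Poisson counts.

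**Assumptions, because the documents are silent.** These are flare duration, daily severity profile, a zero score between flares, and (step 5) timing jitter with SD 2 days.

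**1. The plan's own figures.** Let B and P be the baseline and post-treatment totals. With person effects fixed, the rate ratio is (P/3)/B and SE² = φ(1/B + 1/P), where φ = max(1, X²/14). The degrees of freedom are 20 - 5 - 1 = 14. With 100,000 data sets:

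| Quantity | Stated | Reproduced |
|---|---|---|
| Two-sided error | 4.9% | 4.8% |
| One-sided error | 3.4% | 3.4% |
| Power at 87.5% reduction | over 91% | 91.1% |
| Power to show at least 30% | 80% | 80.2% |

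**2. Calendar fit.** Visit 4 to Visit 8 is 3 × 28 = 84 days. Three cycles need 3 × 35 = 105 or 3 × 42 = 126 days. Even with every visit as late as allowed, 84 + 5 + 5 + 7 = 101 days, which is short of 105. Complete cycles at 84 days: 84/35 = 2.4 and 84/42 = 2, so two each. If logs stop at Visit 7 (56 days): 56/35 = 1.6 and 56/42 = 1.3, so one each.

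**3. Natural-cycle reading.** The same test at n=5 with an 87.5% reduction has power of about 79% if all five supply two post-treatment cycles, and about 18% if all supply one. Data sets with every post-treatment score zero count as no rejection, because this test cannot be computed for them.

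**4. Monthly-window reading, random phase.** For a flare of d days at constant severity, the share of 28-day windows that miss it is 1 - (28 + d - 1)/L.

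| d | L = 35 | L = 42 |
|---|---|---|
| 1 | 1 - 28/35 = 20% | 1 - 28/42 = 33% |
| 3 | 1 - 30/35 = 14% | 1 - 30/42 = 29% |
| 7 | 1 - 34/35 = 3% | 1 - 34/42 = 19% |

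This share is the expected fall in the mean maximum with no drug effect. A 7-day flare with rising and falling severity gives 11% and 26%.

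**5. Monthly-window reading, first dose at the nadir.** The neutrophil peak falls L - 15 days after the first dose and then every L days. With three windows the no-drug fall for 5- and 6-week cycles is 33% for a one-day peak, about 13-23% for an 8-day flare with rising and falling severity, and about 5-13% for an 8-day flare at constant severity. It is 0% if constant-severity symptoms run from neutrophil peak to eosinophil peak without jitter. With two windows the range is 0% to about 50%. At L = 28 the fall is 0%. At L = 21 a window can hold two flares, which pushes the maximum up.

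**6. False benefit (one direction, no drug effect).** If all subjects have 5- or 6-week cycles and three windows are used, the rate is about 4-10% at n=5, against 3.4% under the plan's own null. At n=12 it is about 6-23%, against about 4% when the windows cause no fall. With cycle lengths spread over 4-6 weeks at random phase, it is about 4-6.5% at n=5 and 5-11% at n=12.

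**7. Effect on the estimate.** A true reduction r combined with a calendar fall f is seen as 1 - (1 - r)(1 - f). For r = 87.5% and f = 33%: 1 - 0.125 × 0.67 = 92%. For r = 30% and f = 20%: 1 - 0.70 × 0.80 = 44%.

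**8. Sum of DAES.** If the baseline is one whole cycle and the post-treatment windows are 28 days, the expected no-drug fall is 1 - 28/L, which is 20% to 33% whatever the flare duration.

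**The case against.** The strongest reply is that no section calls the post-treatment cycles 28-day windows. Sections 6.3.4 to 6.3.6 schedule doses and visits, not analysis periods. Elsewhere the plan uses the word biologically: section 15.1 ties the first cycle after baseline to the first eosinophil peak after treatment. With natural cycles there is no spurious fall, and a model with one fixed effect per person accepts unequal numbers of cycles. The plan's schedules also assume a 4-week cycle, at which the problem disappears. The trial is a proof-of-principle pilot that expects a very large effect.

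Most of this stands, and it limits the point. It does not remove it. The natural-cycle reading gives two values where the power calculation has three, and it needs a way to find cycles after dosing. Section 6.3.3 allows that the drug may change cycle times, and section 6.3.4 ends the home blood counts at Visit 6, so later cycles could be located only from the symptoms being scored.

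A reader might go further and infer that the plan builds in a fixed spurious reduction of about 25-38% for 5- and 6-week cyclers. The documents do not support that. The monthly window is an inference, and flare duration and shape are not given. Those two percentages correspond to an effective 26-day window (1 - 26/35 = 26%, 1 - 26/42 = 38%), which appears nowhere in the plan.

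**Conclusion.** The point holds as a defect of definition with a measurable consequence on either reading. It should be fixed, but it does not overturn the design.

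- **Natural cycles:** 5- and 6-week cyclers supply two post-treatment values. Power at n=5 is about 79% if all five are such subjects, against the stated 91%, and there is no bias.
- **Monthly windows:** the no-drug fall in the mean maximum is roughly 0-33% with three windows and up to about 50% with two. It is zero for 4-week cyclers. The position within these ranges depends on flare shape, duration and timing, which are assumptions here.

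The share of subjects with 5- or 6-week cycles is not stated, so the all-long-cycle figures are the upper end. An effect near 87.5% would be seen in either case. What is at risk is the size of the estimate, the lower end of its confidence interval and a conclusion of modest benefit. Under monthly windows the sum-based sensitivity analysis shares the bias, so it would not expose it.

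**What to change.** Before analysis, define windows by L, the subject's own cycle length as determined before treatment:

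- The baseline is the L days before Visit 4. Post-treatment windows are consecutive complete L-day blocks from Visit 4. Use them for both the maximum and the sum. The block boundary at Visit 4 falls at the eosinophil nadir, and no cycle has to be detected after dosing.
- Let the quasi-Poisson model take unequal numbers of blocks per subject, and restate power for subjects who supply two.
- Reconcile the end of daily logging. Stopping at Visit 7 leaves one complete block for 5- and 6-week cyclers (power about 18% at n=5 if all supply one); running to Visit 8 gives two at nominal visit spacing.
- Check that logging starts at least L days before Visit 4. Enrollment at Day -15 with Visit 4 at Day 15 gives about 30 days, short of 35 or 42. Under that schedule enrollment would have to be by Day -20 (35 - 15) or Day -27 (42 - 15), which is inside the Day -30 to -15 range of Table 1.

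The cost is analysis-plan wording, a slightly lower stated power and some unused log days at the end of follow-up. If the drug changes cycle length, fixed L-day blocks will not follow the new cycle, but the comparison still covers equal time before and after treatment.
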